5.5. Analysis Plan

The primary analysis will be performed using the intention-to-treat principle so that all randomized patients will be included in the analysis. The t-test or the Mann-Whitney test will be used if the t-test assumptions are violated. Secondary endpoints of subjective comprehension, anxiety, satisfaction, and information location will be analyzed with the Mann-Whitney test. The binary outcome of consent rates will be compared using the Fisher exact test. The above unadjusted analyses will be complemented by analyses that adjust for potentially confounding

variables in regression analyses. Generalized estimating equations (GEE)⁵⁰ will be used to control for effect of confounding variables (e.g., patient demographics, health literacy level, strata) and a potential consenter effect (as more than one clinician could be involved in the consent process at a clinical trial site). GEE with identity link will be used for comprehension, anxiety and satisfaction analyses. Information location will be analyzed with LOG link and LOGIT link with accrual outcome. Variance will be estimated with the sandwich estimator if the number of consenters is > 30; otherwise the “leave-one-consenter-out” jackknife variance estimation will be used.⁵¹ Exact logistic regression will be used with accrual if the problem of small counts appears. Otherwise Wald tests will be used for significance testing. All two-way interactions between the group indicator (ETRIC vs. standard) and confounding variables will be tested and added to the model if significant. It is expected that all confounders will be analyzed as fixed effects except for the consenter which will be the repeated factor in the GEE. The form of continuous predictors will be either linear, quadratic, or categorized depending on the number of clusters observed in the dataset. Every category in categorical variables will have at least 10 subjects otherwise we will consider merging with neighboring categories. The presence of missing data in excess of 10% will be addressed by developing an imputation model for missing components given the observed part. Then, the multiple imputations approach will be used to estimate regression parameters and their standard errors.⁵²

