Alternative analyses: To satisfy model assumptions we will consider the use of monotone variance-stabilizing transformations for continuous variables. If, however, the model specification continuous being inadequate (non-Gaussian distribution of model residuals, outliers, etc.), we proceed with generalized estimating equations (GEE) instead of the mean linear regression. To accommodate potential dependence of responses within clinical trial sites “leave-one-site-out” cross-validation will be used to estimate robust standard errors of the test statistic (the regression coefficient of the ETRIC effect in either mean or median regression models).

Secondary Endpoints and Final Analysis:

Secondary continuous endpoints are subjective comprehension, anxiety, satisfaction, and information location. The only secondary binary endpoint is the consent rate for the parent clinical trial.

Analysis of secondary endpoints: By analogy with the primary endpoint, the secondary endpoints (1) subjective comprehension scores on the Quality of Informed Consent (part B) instrument, (2) the modified Deaconess Informed Consent Comprehension Test instrument, (3) state anxiety scores on State Trait Anxiety Inventory instrument, (4) overall satisfaction score will be analyzed using t- or Mann-Whitney tests as appropriate. The analysis of time to information location will be performed with generalized linear models (GLM) models using the LOG link function if nonlinearity needs to be accounted for. The comparison of consent rates between ETRIC and standard consent forms will be performed with GEE using the LOGIT link. The GEE model will control for the fixed effect of trial protocol and for the dependence within the clinical trial site. The statistical significance of the ETRIC intervention on each of the secondary endpoints will be declared if the P-values of two-sided Wald test with robust standard errors <0.05. Missing data will be treated by analogy with the primary outcome using multiple imputations and tipping-point analysis.

Patients to Include:

All patients who completed the Quality of Informed Consent (part A) survey will be included in the primary data analysis. All enrolled patients will be included in the data analysis of secondary endpoints.

Content of Tables

Tables:

Table 1: Demographics and baseline characteristics by treatment arm

Table 2: Study endpoints by treatment arm

Table 3: Interaction analyses for the Quality of Informed Consent (part A)

NCT02081248

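### The consent-rate test relies on site-clustered robust standard errors that the SAP does not define, with no small-cluster rule, so its type I error exceeds 5% if sites are few

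*SAP*

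**What the plan says.** **Protocol, section 5.5.** The unadjusted comparison is exact: "The binary outcome of consent rates will be compared using the Fisher exact test". Adjusted GEE analyses are added, in which "all confounders will be analyzed as fixed effects except for the consenter which will be the repeated factor in the GEE". The variance rule depends on the number of clusters: "Variance will be estimated with the sandwich estimator if the number of consenters is > 30"; otherwise one consenter is left out at a time and "jackknife variance estimation will be used". Exact logistic regression is held ready for the consent outcome if counts are small. Otherwise the tests are Wald tests, and no t reference is mentioned.

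**SAP, Analysis of secondary endpoints.** The GEE is now the comparison itself: "The comparison of consent rates between ETRIC and standard consent forms will be performed with GEE using the LOGIT link". On clustering: "The GEE model will control for the fixed effect of trial protocol and for the dependence within the clinical trial site". Significance for each secondary endpoint "will be declared if the P-values of two-sided Wald test with robust standard errors <0.05". There is no threshold on the number of clusters, and the consenter, Fisher's test and exact logistic regression are not mentioned.

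**SAP, Alternative analyses (primary endpoint).** A leave-one-site-out estimate of robust standard errors is named here, for the ETRIC coefficient in mean or median regression. The secondary-endpoint paragraph does not refer to it.

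**Number of sites.** Neither document states it. Protocol sections 2.2.1 and 5.7.1 imply at least 5 centers in the randomized study.

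**The concern.** Cluster-robust inference has two weaknesses when clusters are few. The sandwich standard error tends to be too small, and the normal reference ignores that the variance is itself estimated from only a handful of independent units. Randomization within site does not remove either problem.

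The protocol guards against the first weakness with its 30-cluster condition and against sparse counts with exact methods. Section 5.5 says more than one clinician may obtain consent at a site, so sites should not outnumber consenters. A small-cluster rule therefore matters at least as much once clustering is on site, yet the SAP has none for this test. At stake is a named secondary endpoint: a difference in consent rates between the two forms could be declared more often than the nominal 5% implies.

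**Working it through.** **Inputs from the documents.** Two-sided alpha 0.05 (SAP); logit GEE with site clusters and protocol fixed effects (SAP); 1:1 randomization stratified by center and parent protocol (protocol 5.1.2); about 19 patients from 0901 and about 100 from 1203 (Appendix G).

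**Total N, reproduced from protocol 5.2.** 64 per arm for the t-test; 64 / 0.864 = 74.07, so 74 per arm or 148 in total; 148 / (1 - 0.25) = 197.3, so 198. The plan gives no type I error figure for the consent-rate test beyond its nominal 5%.

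**Assumptions.** Number of sites K from 5 to 40; consent rate 70-80%; site variation moderate (for example intraclass correlation 0 to 0.15, or a site SD of 0.5 on the logit scale); equal or unequal site sizes; permuted blocks within site by protocol; the remaining 198 - 19 - 100 = 79 patients split 40/39 between 1101 and 1301.

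**Step 1: the reference distribution alone.** Suppose the standard error were adequate but estimated from K sites, so that the statistic behaves like t on K - 1 df. Using 1.96 then gives a type I error of P(|t(K-1)| > 1.96):

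- K = 5: 12.2%
- K = 6: 10.7%
- K = 10: 8.2%
- K = 15: 7.0%
- K = 20: 6.5%
- K = 30: 6.0%

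**Step 2: simulated null trials.** Two-sided rejection rate at nominal 5%:

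| Sites | Sandwich, normal | Leave-one-site-out jackknife, normal | Jackknife, t(K-1) |
|---|---|---|---|
| 5-6 | 14-18% | about 11-12% | about 4-6% |
| 10 | 10-12% | 7-8% | about 4-6% |
| 15 | 7-9% | 6-7% | about 4-6% |
| 20 | 6-9% | 5-7% | about 4-6% |
| 30 | 6-7% | about 6% | about 4-6% |
| 40 | 5-7% | about 5% | about 4-6% |

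The lower end of each sandwich range is mostly equal site sizes and the upper end unequal sizes. Monte Carlo error is about 0.4-0.7 points per cell in the main runs (3,000 replicates; for example √(0.05 × 0.95 / 3000) = 0.4 points).

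**Step 3: reading the columns.** The middle column is close to Step 1, so the jackknife largely repairs the standard error and what remains comes from the normal reference. At 10 sites the jackknife recovers about 2-3 points; the t reference is needed for the rest.

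**Sensitivity.** An exchangeable working correlation gives similar sandwich results (10.3% at 10 equal sites, 7.0% at 20 unequal sites). Adding site-by-arm variation (SD 0.5 on the logit scale, unequal sizes) gives 11.7% at 10 sites and 8.5% at 20. A Wald test that ignores clustering stays at about 3-6% when the effect does not vary by site, because the arms are balanced within site.

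**The case against.** The strongest reply is that the SAP never commits to the ordinary sandwich. It names a leave-one-site-out estimate of robust standard errors just before, opens the secondary-endpoint paragraph by analogy with the primary endpoint, and uses the same term again. On that reading the protocol's leave-one-out idea has moved to site along with the clustering. This stands as far as it goes: the text is ambiguous. But the earlier sentence belongs to the primary endpoint's fallback analyses and to mean or median regression, and a logit GEE is neither. Even on the generous reading, a jackknife with a normal reference exceeds 5% when sites are few.

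A reader might also infer the following, which the documents do not support:

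- **That error is well above 5% in this trial.** The number of sites is unknown. The excess is large at 5-10 sites, moderate at 15-20 and small at 30 or more.
- **That restoring the protocol's rule would cure it.** The protocol pairs its jackknife with Wald tests and gives no t reference, so the rule moved to site level would still give 7-8% at 10 sites.
- **That moving from consenter to site is an error.** Consenters work within sites, so site clustering also covers dependence within consenter.
- **That the other secondary endpoints are inflated in the same way.** Four scores are assigned t- or Mann-Whitney tests, and information-location time a GLM with no stated site clustering. Site dependence is specified only for consent rate. The blanket Wald criterion does conflict with the t- and Mann-Whitney wording, but that is a matter of consistency.

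Consent rate is also the last of five secondary endpoints, and protocol section 2.1.4.2 describes it as exploratory. That limits the weight of the point.

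**Conclusion.** The concern holds for one secondary endpoint. The SAP leaves both the variance estimator and the reference distribution of the consent-rate test undefined, and drops the protocol's cluster-count condition and exact methods without replacing them. Either available meaning of 'robust', used with a normal reference, rejects too often when sites are few: the ordinary sandwich by about 9-13 percentage points at 5-6 sites and 5-7 at 10, the jackknife by about 6-7 and 2-3. By 30 sites the excess is only 1-2 points.

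These sizes rest on assumed consent rates, site variation, site sizes, block size and number of sites. The SAP is dated September 2016, after enrollment closed in August 2016, so the sponsor could have settled the last of these. The primary t-test or Mann-Whitney analysis is not affected.

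**What to change.** 1. State the number of randomizing sites in the SAP, and say why clustering moves from consenter to site.
2. If there are 30 or fewer sites, define the robust standard error for the consent-rate GEE as the leave-one-site-out jackknife, referred to a t distribution on (sites - 1) degrees of freedom.
3. Keep Fisher's exact test as a stated check, or exact logistic regression if refusals are few.
4. Limit the Wald criterion to the model-based secondary endpoints, so that the scores assigned t- or Mann-Whitney tests are judged by those tests.

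The cost is SAP wording, a few lines of code and slightly wider intervals for the consent-rate comparison. No new data are needed.
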